#### Child:

- (a) living with foster carer(s) in a placement planned to be at least 4 months;
- (b) lived with foster carer for at least 4 weeks
- (c) presence of DSM-5 defined RAD\*
- (d) aged between 11 months and 6 years

Note: as outlined below, because of the uncertain prevalence of RAD in UK foster care populations, the RAD eligibility criterion will be reviewed after 15 cases have been assessed. If fewer than 3 (out of 15) cases scoring over the screening threshold (> 66th percentile on screening measure) actually meet diagnostic criteria, we propose to include sub-diagnostic cases with elevated symptoms in the feasibility trial based on the screening threshold (defined below).

For the pilot case series, we will include a mix of cases that meet the RAD diagnosis and those falling short of the diagnostic threshold in order to explore the suitability of the intervention for both groups of children and expedite the rapid progress of manual refinement.

\*If during the RCT phase number of participants deemed eligible is inadequate to allow delivery of the final study aim (i.e. run the modified VIPP programme for foster care) we will expand the eligibility criteria to include carers with children who do not necessarily meet the RAD criterion.

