#### 6.3 RANDOMISATION (PHASE 3)

Participants will be individually randomised in a 1:1 ratio to one of the two treatment arms, CAU + VIPP-FC or CAU-only. Randomisation with minimization will be employed, with minimization factors age (<=4 versus >4), gender and site. Minimization will include a random factor, as implemented in the minimisation program Simin (Wade, Pan, Eaton, Pierro & Ong, 2006). Randomisation will be requested by a member of the research team following completion of all necessary screening and consent procedures, and will be performed by an unblinded member of the trial coordination team. The allocation list will be held in the Trial Master File. We will write to the child's social worker, and VIPP intervener – the latter for those allocated to VIPP-FC. The foster carer, and the individual(s) giving consent on behalf of the child (the parent and/or local authority social worker with parental responsibility as appropriate, see consent section) will be notified of the outcome by letter by the unblinded member of the trial coordination team. The foster carer will also be contacted by telephone (target within 24 hours) to ensure a timely initiation of intervention.

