# **10** ANALYSIS

Feasibility parameters based on proportions (proportions of cases identified, consented, randomised, completing treatment and outcome measures). Approximate variance estimates will be obtained for the main outcome measures using the upper 80th percentile of the relevant confidence interval (see Brown, 1995). Specifically, we will test the following feasibility parameters:

A. Test the feasibility of identifying sufficient numbers of appropriate cases using screening instruments.

1. Target N for screening tests returned N = 500. Test a.1 = proportion and 95% CI of those returning screening instruments from total sent out.

2. Target N of diagnostic assessments N = 100. Test a.2 = proportion and 95% CI of positively screened cases (above upper 66th percentile) agreeing to full assessment.

3. Target N for positive diagnosis from upper 66th percentile of screened cases N = 50. Test a.3 = proportion and 95% CI of cases where diagnosis is confirmed.

4. Test a.4: initial test of false negative rate = proportion (of 25 cases) and 95% CI of detected diagnoses in random sample of cases not meeting screening threshold.

5. Initial non-parametric ROC curve analysis (total N = 125), based on assumption that DAI diagnosis is gold standard.

B. Test the feasibility of recruiting/consenting foster families with children with RAD to an RCT.

1. Target N of consented cases N = 40. Test b.1 = proportion and 95% CI of cases consenting to enter pilot trial from those meeting entry criteria.

C. Investigate feasibility of randomising to VIPP-FC or CAU.

1. Test c.1: proportion and 95% CI of cases accepting randomisation.

D. Document study throughput.

1. Test d.1: proportion and 95% CI of cases randomised completing treatment (definition of completing= 80% of offered sessions).

2. Test d.2: proportion of cases attending each session (6 proportions and 95% CIs).

4. Acceptability of treatment: means and ranges of client satisfaction survey. See also qualitative methods for client experience of treatment interviews.

E. Establish the feasibility and acceptability of baseline and outcome assessments.

1. Test e.1: proportion and 95% CI of cases with complete data. See also qualitative methods for client feedback regarding measures.

F. Identify the most appropriate primary outcome. Key assessment is participant feedback from qualitative interviews. However preliminary tests from H.2 below may also be informative.

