G. Obtain initial estimates of variance of key outcome measures and constrain effect size estimates for future power analyses.

- 1. Test h.1: S.D. of RAD symptom counts and 95% CI.
- 2. Test h.2: Mean post-treatment group difference and 95% CI (though please see point 8 above).

H. Establish the optimal and most acceptable screening tools for RAD as recently redefined in DSM-5. Tested with qualitative interviews and tests a.4 and a.5 above.

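### Test h.2 should not help choose the primary outcome, and h.1 and h.2 need reporting by diagnostic status if eligibility is widened

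*Protocol*

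**What the plan says.** **Planning estimates.** Section 10, item G, gives two tests: "Test h.1: S.D. of RAD symptom counts and 95% CI" and "Test h.2: Mean post-treatment group difference and 95% CI", the second with a bracketed caveat that refers back to a point 8. Their stated purpose is to estimate variance and to "constrain effect size estimates for future power analyses". Section 10 opens with a rule for the variance: "Approximate variance estimates will be obtained for the main outcome measures using the upper 80th percentile of the relevant confidence interval".

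**Choice of primary outcome.** Section 10, item F, names participant feedback from interviews as the key assessment and then says: "However preliminary tests from H.2 below may also be informative". Item H of section 10 concerns screening tools and has no numbered tests, so this can only mean test h.2. Section 7.2 already places the DAI under a primary-outcome heading, while the section 4.2 aims for Phase 3 treat the choice as still to be made.

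**Who may be in the sample.** Section 4.4 requires DSM-5 RAD but has two routes to widening. If fewer than 3 of the first 15 assessed children are diagnosed, sub-diagnostic children above the screening threshold are admitted. If numbers prove inadequate during the trial, "we will expand the eligibility criteria to include carers with children who do not necessarily meet the RAD criterion". Section 10 does not say how h.1 and h.2 are reported in either case.

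**Allocation.** Section 6.3: "Randomisation with minimization will be employed, with minimization factors age (<=4 versus >4), gender and site".

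**The concern.** The pilot is meant to hand a variance and an effect size to the full trial. Two features of the text could damage them.

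First, a between-arm difference is allowed to bear on which outcome becomes primary. An outcome preferred partly because its pilot difference was large will, on average, have been helped by chance. The same difference then enters the power calculation, so the full trial could be too small.

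Second, if children without RAD are admitted, one SD and one mean difference describe a mixture. Section 3 describes the full trial as being in children with RAD, so the SD for the mixture may not be the one needed.

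**Working it through.** **Inputs from the protocol:** 40 randomised, 20 per arm (General Information); 75% outcome completion, 30 of 40 (section 6.1), so about 15 per arm; RAD score 0 to 10 (section 7.2). No SD, effect size or correlation is given, so those used below are assumptions.

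**Check on the plan's own figure.** The exact (Clopper-Pearson) 95% interval for 30/40 is 58.8% to 87.3%, which reproduces the stated 59% to 87%. The protocol gives no precision figure for h.1 or h.2.

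**Precision of h.2 in SD units.** Half-width = t(0.975, 2n−2) × √(2/n).
- n = 20 per arm: 2.024 × 0.316 = 0.64.
- n = 15 per arm: 2.048 × 0.365 = 0.75.

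**Can h.2 rank two outcomes?** For two outcomes on the same children with correlation ρ, the half-width for the difference between their standardised effects is about the figure above × √(2(1−ρ)).
- ρ = 0.5: factor 1, so 0.64 (40 analysed) to 0.75 (30 analysed).
- ρ = 0: factor 1.414, so 0.91 to 1.06.

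Only very large differences between outcomes could be told apart.

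**Upper bound on the selection effect.** Suppose the outcome were chosen purely by the largest h.2 among eight measures, none with a true effect. (The section 7.2 table has eight repeated measures besides CA-SUS.) The mean maximum of eight standard normals is 1.42 if independent and 1.01 at ρ = 0.5. Multiplying by SE(d) = √(2/15) = 0.365 gives an apparent d of 0.52 and 0.37. The protocol states no such rule, so the real effect would be smaller.

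**How likely is widening?** Probability of fewer than 3 diagnoses in 15, by true proportion diagnosed among screen-positive children:

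| True proportion | P(fewer than 3 of 15) |
|---|---|
| 50% | 0.4% |
| 30% | 12.7% |
| 20% | 39.8% |
| 10% | 81.6% |

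This covers the first route only. Section 6.1 itself calls the 50% uncertain.

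**Effect of a mixture on the SD.** With equal within-group SDs, a fraction π of non-RAD children and a mean gap of D within-group SDs, the overall SD is multiplied by √(1 + π(1−π)D²), and N by the square of that.

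| D | SD, π = 0.5 | N, π = 0.5 | SD, π = 0.2 | N, π = 0.2 |
|---|---|---|---|---|
| 0.5 | +3% | +6% | +2% | +4% |
| 1 | +12% | +25% | +8% | +16% |
| 2 | +41% | +100% | +28% | +64% |

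Unequal SDs can reverse the sign. Take assumed SDs of 2 (RAD) and 1.5 (non-RAD), mixed half and half. The mixture variance is 0.5×4 + 0.5×2.25 + 0.25×gap².
- Gap 4 points: 7.125, and 7.125/4 = 1.78, so N is 78% too high.
- Gap 1 point: 3.375, and 3.375/4 = 0.84, so N is 16% too low.

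**The existing 80% rule.** It multiplies the SD by 1.12 (38 df) or 1.14 (28 df). It allows for sampling error in the SD, not for a change of population.

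**The case against.** The best defence on outcome choice is that item F makes qualitative feedback the key assessment and says only that h.2 may be informative. It states no rule for picking the largest effect, names no set of eight outcomes, and h.2 follows directly on a test of RAD symptom counts. That stands, and it is why the selection figures are an upper bound. It does not rescue the sentence: h.2 is too imprecise to inform the choice. The caveat attached to h.2 gives no protection either, because section 10 has no point 8.

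On mixing, three replies have force. Widening is conditional. The first route admits children above the screening threshold, who need not be near the floor of the score; only the second route states no symptom requirement. And if the full trial adopted the widened criteria, the overall SD would be the right one. These limit the size of the point and argue for reporting both estimates. A practical limit also stands: the first route opens only when diagnoses are scarce, so the RAD-confirmed stratum may be small.

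A reader might go further and infer that h.1 and h.2 are raw estimates that ignore the baseline DAI and the minimisation factors. The protocol does not say so. An adjusted estimate is also a mean post-treatment difference, and the model and the way the SD is formed are commonly left to a statistical analysis plan, which is not at hand. The unadjusted difference would in any case be unbiased. The precision gain from adjustment depends on an unknown correlation, which may be low because children are selected on the same DAI.

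**Conclusion.** Two limited points hold.

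1. Item F gives a pilot between-arm difference a part in choosing the primary outcome. Its half-width is 0.64 SD if all 40 are analysed and 0.75 SD at the protocol's 75% completion. The bias in the effect carried forward grows with the weight given to h.2 and cannot be quantified from the text. Item F also sits awkwardly with section 7.2, which already names the DAI as primary.
2. If eligibility is widened, a single h.1 and h.2 may misstate the SD for a full trial in RAD. For a half-and-half mix with equal within-group SDs, N rises by about 6%, 25% or 100% at gaps of 0.5, 1 or 2 SD. The mix, gaps and SDs are all assumed; the 78% case is a wide-gap example and should not be quoted alone. The randomised comparison is not biased.

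The documents do not support a finding that the analysis omits covariates. On that the protocol is silent, not wrong.

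**What to change.** - Delete the H.2 sentence from item F. Base the choice of primary outcome on acceptability, completeness, reliability and floor effects, and reconcile item F with the labelling of the DAI in section 7.2.
- Correct or remove the reference to point 8 in test h.2.
- If eligibility is widened under either route in section 4.4, report h.1 and h.2 by diagnostic status alongside the overall estimate, and note that the strata may be small.
- Optional: state that h.2 is adjusted for the pre-randomisation DAI and the minimisation factors, with site collapsed to region.

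The first three are wording and reporting changes that need no extra participants, visits or measures; the strata estimates will be imprecise. The optional item costs a few degrees of freedom.

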# **Qualitative Data Analysis:**

Following full transcription, the qualitative data will be entered into NVivo3 and analysed using thematic analysis in two stages that will involve the introduction of codes across the data followed by further examination of the coded data extracts to identify patterns/themes across the data. The final report will describe the key themes using quotations to demonstrate the findings.

# **10.1** HEALTH ECONOMICS

The health economic component of this feasibility study will involve two main elements. The first will involve modification and testing of an appropriate version of the child and adolescent service use schedule (CA-SUS), which has been successfully applied in a pre-school population with autism (Byford et al., 2015) and is currently being implemented in an evaluation of a mental health screening and early intervention

for under 4s, including looked after children (Murphy, 2016). These versions of the CA-SUS will form the basis of a modified version suitable for the current population, with modifications being determined initially by expertise in the research group and subsequently by testing for acceptability and comprehensiveness in the proposed pilot study. Specifically, this initial draft version will then be tested and modified in two main ways. First, we will assess respondents' understanding of the questions and modify the wording or add explanation if anything is unclear. Secondly, we will assess the measure's comprehensiveness in capturing all relevant services. Testing may identify items which are redundant or important services that have been omitted. The CASUS is used as an interview and in the feasibility stage researchers will probe for any missing items and explore (and record) contact with certain key services, such as CAMHS, local authority services and charities about the nature of the contact. The second component will involve exploration of recent literature to assess how realistic it might be to include a measure of health-related quality of life capable of generating quality adjusted life years (QALYs) in this young age group. Without such a measure, it is difficult to make clear resource allocation decisions. However, no measure currently exists for children under 7 years old and although we are aware of research exploring this issue, results are not yet available and are unlikely to be of value for infants and very young children. Review of the most recent evidence may highlight possible solutions, although we do not anticipate there will be a perfect solution for the full age range of 0 to 6. Any subsequent full RCT will therefore be reliant on cost-effectiveness analysis, focusing on the primary clinical measure of outcome.

# 11 PROJECT MANAGEMENT

The project will be led by [name] as Chief Investigator, who will retain overall responsibility for the management of the study, including governance, financial oversight and progress reporting. [name] will take responsibility for day-to-day supervision of the research assistant and trial management team, with input from [name]. Each collaborating trust will have a Core study team member allocated to it, who will manage relationships, recruitment set-up, monitoring and communications with their trust and its associated local authorities, with input from the CI where appropriate. [name] will cover CNWL, [name] SLAM, [name] NELFT, [name] LYPFT and TEWV, and the Tavistock and Portman will be jointly overseen by [name] and [name]. This Core Study Team will meet regularly to ensure coordination and monitoring of the practical implementation of systems for recruitment, and the establishment and monitoring of the clinical service delivery of VIPP in each locality. The trial management team will take responsibility for liaison with the sponsor and ethics committees, setting up secure data capture systems for multi-site data collection, and preparing data quality and progress reports for the Steering Committee and HTA. [name] will chair the expert and carer group advising on clinical manual development, and advise on trial design and implementation. [name] will work closely with the CI in preparing the pilot trial from the point of view of implementation within a foster care setting, as well as

contribute to the work of the treatment manual development group. [name] will provide expert input to the treatment development group, and will oversee the measurement aspects of the RAD screening system. [name] will manage the qualitative/mixed methods evaluation. [name] will lead the carer and care-leaver advisory groups, contribute to the expert and carer advisory group and provide regular input to the core study team regarding foster carers' perspectives on study measures, information sheets and clinical process. There will be quarterly full team meetings at which all investigators would be present.

# 11.1 GOVERNANCE:

A Steering Committee will be established which will include senior researchers and practitioners with experience in treatment development studies and trials and PPI representatives. The steering committee will meet up to five times and will be used to monitor the progress of the project and advise the research team on matters arising during subsequent phases of the study. The committee will be chaired by an independent senior researcher with extensive experience in the field. The steering committee will receive reports on serious adverse events and data quality from the trial coordinating team.

# 12 **DISSEMINATION**

Our team has a very strong track record of dissemination through publication, policy documents, advisory groups (including NICE and NHS England) and service development and presentations to academic, clinical, policy and public audiences, in the UK and internationally. We will disseminate research outputs to the following key audiences

1) Academic dissemination: This will include publication of the manual and its development process, a paper on the multiple test case series, a policy/implementation paper on practical barriers and solutions to running attachment-focused trials in the foster care setting, the pilot trial protocol, and the results of the pilot trial. We plan for members of the team to attend two international academic conferences.

2) Foster carer and general public audiences: We will disseminate findings through our institutional websites, a designated project website and through our partner organization the NSPCC. Members of our PPI group will attend, with members of the study team, two national foster care and/or social work conferences such as the British Association of Adoption and Fostering (BAAF). Our findings will be fed back through local meetings with foster care and adoption organizations and agencies (e.g., By The Bridge Fostering, TACT Fostering, Coram), and local authority foster care groups.

3) Clinical and policy audiences: Within local services we will hold regular seminars updating on the progress of the study and later reporting the outcomes of the study. The clinical manual will be made available to participating CAMHS and local authority teams during the study to facilitate dissemination and learning. On a national and international level, we will liaise closely with the NIHR, national organisations (especially the NSPCC) to ensure that national clinical and policy audiences are aware of the project. In addition to academic publications we will also aim to produce a summary publication in a peer-review article for community practitioners, such as Adoption and Fostering. We will also create a short accessible summary of the findings for services, particularly social care services, GPs and CAMHS.

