#### Phase 3: Running a pilot RCT of modified VIPP-FC

The final phase of the study will consist of a pilot RCT, in which a new group of children with RAD (i.e., not those involved in the initial non-randomised clinical pilot series) will be randomised to receive VIPP-FC + Usual Care, versus Usual Care only. Children with RAD will be identified initially using a large community screening process in 6-10 local authorities to identify, at-source, children experiencing high levels of

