
# 5.2 CARE AS USUAL (CAU)

VIPP-FC will be compared to usual care, as there is no pre-existing integrated care pathway for children in foster care. Care as usual varies widely from locality to locality and good data is not recorded that would currently allow precise specification of CAU in a planned trial. Systematically documenting CAU is therefore a key objective of this study. Initial consultations with CAMHS teams in our study sites, identified several likely treatments that may be offered within CAU: 1) Theraplay, 2) 1-3 sessions of foster carer consultation 3) network consultation, 4) Incredible Years, 5) foster carer support, 6) 6-12 sessions of psychotherapy, 7) behaviour support, 8) foster parent groups. As assessments of attachment disorders are rarely undertaken it is not possible to determine the extent to which the type and intensity of services offered to this particular group is different to other young children in foster care referred to CAMHS. We will use the Child and Adolescent Service Use Schedule (CA-SUS) to systematically describe and quantify the services received by children and carers in the comparator arm of the pilot trial, as well as detailed qualitative information from the scoping study (Phase 2b). The CA-SUS will ask participants to confirm whether they have attended any health services, mental health services, support services or childcare services and if so how many times they have attended these services in the last 6 months.

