# 5.3 TRAINING

We will train a group of individuals from each NHS Child and Adolescent Mental Health Service (CAMHS) team involved in this study, as well as other appropriately qualified practitioners from other providers, in delivery of the VIPP-FC intervention. Each intervener will be trained by an accredited trainer, and will undertake supervised practice before becoming a study therapist. Accredited supervision will be provided to all practitioners during the pilot case series and feasibility trial.

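### Releasing the VIPP-FC manual to CAMHS and local authority teams during the study creates an avoidable risk that its content enters the care-as-usual arm

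*Protocol*

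**What the plan says.** The protocol's section 12 (Dissemination), under clinical and policy audiences, says of the manual: "The clinical manual will be made available to participating CAMHS and local authority teams during the study to facilitate dissemination and learning". It adds, for the same services: "Within local services we will hold regular seminars updating on the progress of the study and later reporting the outcomes of the study". The recipients are teams, and the stated purpose is dissemination and learning, not delivery of the trial intervention.

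Section 4.2 (Phase 3) says that children "will be randomised to receive VIPP-FC + Usual Care, versus Usual Care only". Section 6.3 fixes the unit of allocation: "Participants will be individually randomised in a 1:1 ratio to one of the two treatment arms, CAU + VIPP-FC or CAU-only", with "minimization factors age (<=4 versus >4), gender and site".

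On the comparator, section 5.2 reports that CAMHS teams at the study sites "identified several likely treatments that may be offered within CAU". The eight types listed include foster carer consultation, foster carer support, behaviour support and foster parent groups. The same section makes systematic documentation of CAU a key objective. Section 5.3 says: "We will train a group of individuals from each NHS Child and Adolescent Mental Health Service (CAMHS) team involved in this study", together with practitioners from other providers.

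**The concern.** A pilot that sets out to describe usual care should avoid changing it while it is being measured. Section 4.2 (Phase 2b) explains that no comprehensive account of usual care for these children exists, which is why the CAU description matters so much here. If the services that make up CAU receive the experimental manual while control families are still under follow-up, part of what is recorded as usual care may be a product of the trial.

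The second thing at stake is item G of section 10. It plans a post-treatment mean difference with a 95% confidence interval, to help constrain effect sizes for later power calculations. Any VIPP-FC content used with control families would tend to pull that difference towards zero.

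The protocol is aware of the general problem. Section 4.4 gives contamination as one reason for excluding families already engaged in a similar parenting intervention. That rule acts on the family at entry. It does not cover transfer through staff after randomisation.

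**Working it through.** The protocol states no figure on this point, so the check sets its passages side by side. The arithmetic only shows what the pilot could and could not detect.

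1. **Who gets the manual, and when.** Section 12: participating CAMHS and local authority teams, during the study. No date, embargo or restriction to interveners is written.

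2. **Who provides usual care.** Section 4.2 (Phase 2b) says services for children in care tend to come from the local authority, CAMHS and the third sector. The likely CAU treatments in section 5.2 were named by CAMHS teams at the study sites. The first two of these services are the recipients in step 1. The protocol does not say that the same individuals are involved; the overlap is at service and team level.

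3. **Whether both arms sit in the same services.** Allocation is individual and 1:1, and site is a minimisation factor (section 6.3). Minimising on site tends to balance the arms within each site, so control and VIPP-FC families should be found side by side.

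4. **Whether anything blocks the route.** The section 4.4 exclusion applies at entry. Section 5.3 covers training and supervision of interveners. The fidelity checks in section 5.4, read in context, concern VIPP-FC sessions. No section asks staff to keep VIPP-FC material away from control families.

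5. **Whether it would be seen.** Section 5.2 describes the CA-SUS as recording which services were attended and how often in the last 6 months. Section 10.1 goes further: researchers explore and record what contact with key services, including CAMHS and local authority services, consisted of. Some transfer could surface there, but VIPP content is not named as an item. The Phase 2b scoping interviews (September 2017 to March 2018, section 13) fall mostly before or at the start of pilot recruitment (from February 2018), so they mainly describe usual care before this exposure.

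6. **What 20 control children could show.** If VIPP-type content were recorded and none were found, the exact 95% upper limit is 1 − 0.025^(1/20) = 16.8%. Two cases in 20 would give 1.2% to 31.7%. Recording is useful, but it could not rule out material transfer, so prevention counts for more than detection.

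7. **Length of an embargo.** The last outcome assessment is planned for June 2019 (section 13). From this protocol version (16 January 2019) that is about 5 months. From the planned end of manual revision (March 2018) it is about 15 months.

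**The case against.** The strongest reply is that having a manual is not delivering VIPP-FC. The programme is six 90-minute home sessions built on filming carer and child and giving tailored feedback (section 5.1), by staff who have had accredited training, supervised practice and supervision (section 5.3). In addition, some staff in each CAMHS team are trained and must hold the manual, so part of the exposure exists by design. Both points stand. They limit the concern to the increment from wider release, and to the more portable parts of the content, such as recognising attachment signals, praise, and exercises and tips for carers.

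A second reply concerns timing. The study has final analysis months after the last assessment (months 27 to 30), and the final manual is produced only at the end of Phase 3 (section 4.2), so the sentence could mean release after follow-up. That reading is possible, but it is not written and fits poorly with an unqualified reference to the study period.

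A third reply is that the group difference is too imprecise for dilution to matter. With 20 per arm, the 95% half-width on a standardised difference is about 1.96 × √(2/20) = 0.62. Taking d = 0.47 from section 2.1 for illustration only, an assumed 10% to 30% dilution moves it by 0.47 × 0.10 = 0.05 to 0.47 × 0.30 = 0.14. None of the numerical progression thresholds in section 13.1 uses the difference. This stands, and it is why the CAU description carries most of the weight.

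A reader might also infer that contamination would be invisible because the CA-SUS only counts contacts. Section 10.1 does not support that, since what the contacts consisted of is to be explored and recorded.

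**Conclusion.** The point holds as an avoidable risk created by the wording of section 12. It does not show that the comparator is contaminated. It rests on three things the protocol does state (release to teams during the study, usual care provided by those services, and individual randomisation within sites) and on one inference, that control families will meet staff from the teams that receive the manual.

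The size cannot be given. A reader might infer a sample-size penalty for the full trial from 1/(1 − c)², which gives 1.23 at c = 10% and 2.04 at c = 30%. The protocol supplies no value of c. The formula also assumes that each affected control receives the full effect without training, supervision or video feedback, so those multipliers should not be used.

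A reader might also extend the point to two children of one carer being allocated to different arms. That is a separate question about section 6.3, does not follow from the release of the manual, and forms no part of this conclusion.

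**What to change.** Amend section 12 so that, until the last pilot outcome assessment (planned for June 2019), only trained VIPP-FC interveners and their supervisors hold the manual, with release to the wider CAMHS and local authority teams afterwards. Add that, during this time, interveners are asked not to use VIPP-FC material with control families. Record any VIPP-type content received in the CAU arm through the CA-SUS probing already planned in section 10.1.

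One detail needs care. Section 7.3 keeps the research assistant blind to allocation, so the added question should be neutral, put to both arms, and asked after the outcome measures at that visit.

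The cost is a few sentences of protocol text, one interview item, and later sharing of the manual: about 5 months from this version, and up to about 15 months if counted from the planned end of manual revision. Recruitment, sample size and analysis are unchanged. If copies have already gone to wider teams, a log of which teams received them and when would let the CAU data be read accordingly.
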